#### 6. PROTOCOL DEVIATION

Protocol violations will be tracked by the study team throughout the conduct of the study. Data will be reviewed prior to closure of the database to ensure all important violations are captured and categorized.

A major protocol deviation is any significant protocol deviation that threatens the scientific validity of the data collection for a subject or is a serious violation of ethical study compliance and GCP. Examples of major protocol deviations include but are not limited to the following:

• Violation of inclusion/exclusion criteria at enrollment

#### 7. ANALYSIS POPULATION

**Enrolled**: The enrolled population includes all eligible subjects based on the defined inclusion and exclusion criteria.

**Intent-to-Treat (ITT) Population:** All subjects who are enrolled into the study, provide informed consent waiver, and receive study intervention.

**Per-Protocol (PP) Population**: All subjects in the full Analysis Set not identified as major protocol violations.

The endpoints analysis will be based on the Intent-To-Treat population. The per-protocol set will be supportive and will be used to assess the robustness of study results if neccesary. Safety analysis will be based on the Intent-To-Treat population.

#### 8. SAMPLE SIZE DETERMINATION

Subjects from that consecutive series will be included in the study based on the defined inclusion and exclusion criteria, and sample size is not based on hypothesis testing. The planned sample size for this study will be approximately 35 treated subjects.

#### 9. STATISTICAL ANALYSES

#### 9.1 General Statistical Considerations

Descriptive statistics will be used to summarize study outcomes. No formal statistical testing will be performed. The study objectives will be presented by summary statistics.

For categorical data, frequencies and percentages will be provided. For continuous data, descriptive statistics, including sample size, mean, median, standard deviation, and range of values (i.e., minimum, and maximum values) will be provided.

A separate Table Listing Graphs (TLFs) will be provided.

All statistical analysis will be conducted using SAS® for Windows, version 9.4 or later.

#### 9.2 Study Subjects

#### 9.2.1 Disposition of Patients

The disposition of all subjects in the study will be provided for all available data. The numbers of subjects signed informed consent waiver, screen failed, enrolled, completed, and discontinued during the study will be summarized. Disposition and reason for study discontinuation will also be provided as a by-subject listing.

#### 9.2.2 Demographics

Baseline demographics Gender, Age, Race, Nicotine use will be summarized descriptively. By subject listings will be provided for each subject reported.

#### 9.2.3 Medical History

The subject's relevant medical history (up to 3 years prior to surgery) will be summarized and presented by count and percentage of subjects as captured on the CRFs. Types of Body Systems and Category will be summarized by frequency. By subject listings will be provided for each subject reported.

#### 9.2.4 Concomitant Medication

The subject's relevant medication history (i.e. medication taken up to prior to surgery) and relevant concomitant medication (i.e. current medication) will be summarized and presented by count and percentage of subjects as captured on the CRFs. Only immunomodulators and opioids are to be reported. By subject listings will be provided for each subject reported.

#### 9.2.5 Surgery Evaluation

Operative details will be summarized and presented by count and percentage of subjects as captured on the Surgery CRF. These information include but not limited to:

- Ventral Hernia Details: Location and size of the ventral hernia(s), CDC Wound Class (the highest one) and complications associated with Hernia(s) repair.
- Surgery Details: Surgical approach (Robotic, Laparoscopic, Robotic assisted, Laparoscopic assisted, MIS converted to open, Open), Times related to the different steps of the index surgery.
- Type of the Gentrix Surgical Matrix Used.
- Intraoperative Details: Surgical Plane of graft placement, Graft fixation, Component separation, Concomitant procedure, Stoma presence, and Fascial closure.

By subject listings will be provided for each subject reported.

#### 9.2.6 Discharge and Follow-Up Visits

Discharge and Follow-Up Visits details will be summarized and presented by count and percentage of subjects as captured on the CRF. These information include but not limited to:

- Post-operative complications requiring procedural intervention
- Post-operative complications (Surgical Site Occurrences)
- Surgical Site Infections (SSIs)
- Hernia recurrence confirmed by clinical assessment
- Reoperations due to index repair

By subject listings will be provided for each subject reported.

#### 9.2.7 Study Exit

Study exit type will be summarized and presented by count and percentage of subjects as captured on the Study Exit CRFs. By subject listings will be provided for each subject reported.

#### 9.2.8 Time to Hernia Reoccurance Survival Analyses

Time to reoccurance Kaplan-Meier Curve will be provided for all subjects with hernia reoccurance at follow-up visits.

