#### 6.1.4 Follow-Up Visit

The time frame for follow up visits is up to 1 year or shorter, as applicable.

Since previous visit, the patients' data to be collected at the follow-up visit(s) are:

- Post-operative complications requiring procedural intervention
- Post-operative complications (Surgical Site Occurrences)
- Surgical Site Infections (SSIs)
- · Hernia recurrence confirmed by clinical assessment
- Reoperations due to index repair

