#### 5. STUDY PROCEDURE

This retrospective study specifically aims to collect data from the day of the index procedure, and post-operatively up to a maximum of one year or shorter as applicable. Data will be collected via medical records, study worksheets, and entered into electronic data capture system by the site.

Enrollment period will be approximately 1 month. Total duration of the study will be approximately three months.

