#### 9.3.2 Analysis of the Secondary Endpoints

The following incidents by subjects will be summarized: Incidence of early post-operative complications (Surgical Site Occurrences) within 90 days post index procedure (seroma, abscess,

dehiscence, hematoma, wound necrosis, ileus, fistula, delayed wound healing). Incidence of Surgical Site Infections (SSIs) within 90 days post index procedure. Incidence of later post-operative complications occurring after 90 days post index procedure. Incidence of hernia recurrence confirmed by clinical assessment. Incidence of reoperation requirement due to index repair.

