#### 11. MISSING DATA

Reasonable efforts will be made to obtain complete data for all subjects. Nevertheless, given the nature of this study (i.e. Retrospective), it is anticipated that missed visits/evaluations will occur and hence there will be missing data on some of the endpoints. Missing data will not be imputed.

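### The Kaplan-Meier curve for time to recurrence includes only subjects who recurred, so it ends at 0% whatever the recurrence risk in the cohort

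*SAP*

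**What the plan says.** SAP section 9.2.8 consists of one sentence: "Time to reoccurance Kaplan-Meier Curve will be provided for all subjects with hernia reoccurance at follow-up visits". It gives no time origin, event-date definition or censoring rule. The protocol's statistical section (10.4) plans no time-to-event analysis, so nothing there supplements or overrides it.

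Four other places bear on the point:

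- **Population.** SAP section 7 states "The endpoints analysis will be based on the Intent-To-Treat population", meaning the enrolled and treated subjects.
- **Endpoint.** Recurrence is the fourth of five secondary endpoints. SAP 9.3.2 summarises it by subject as "Incidence of hernia recurrence confirmed by clinical assessment", with no time window. SAP 9.2.6 adds counts and percentages.
- **Follow-up.** Protocol 6.1.4 states "The time frame for follow up visits is up to 1 year or shorter, as applicable", and SAP section 5 describes collection "post-operatively up to a maximum of one year or shorter as applicable". Under Protocol 5.1, procedures qualify up to 90 days before data collection starts, so some subjects can have far less than a year of follow-up.
- **Missing data.** SAP section 11 expects missed visits and states "Missing data will not be imputed".

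**The concern.** A Kaplan-Meier estimate is informative because the risk set holds everyone still under observation and free of the event. Recurrence-free subjects, including those with short follow-up, must be counted for as long as they were observed. Section 9.2.8 leaves them out. Once the sample is selected on having the event, the result no longer depends on how common the event is.

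Two things are at stake. First, a reader who finds a recurrence figure under a survival-analysis heading will take it as recurrence-free survival, and this one must show 0% by its end. Its median is only the median delay among recurrers. Second, this is the only planned analysis that could allow for unequal follow-up. The other recurrence summaries are simple proportions, which count a subject last seen at three months and a subject seen at one year alike.

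**Working it through.** The plan gives no recurrence figure to reproduce, and the sample size of about 35 (SAP section 8) is not derived from one. The check applies the estimator to the two candidate populations.

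**Inputs**
- N = 35: "The planned sample size for this study will be approximately 35 treated subjects".
- Maximum follow-up of 365 days: Protocol 6.1.4 and SAP section 5.
- Number of recurrences, k: not given for this device, so assumed. The range is 1 to 11 of 35 (2.9% to 31.4%). The upper end follows the 31.8% at 18.2 months that Protocol 2.1 cites for other biologic materials (0.318 × 35 = 11.1).
- Recurrence days: assumed, spread evenly over days 60 to 350 (day 200 when k = 1).

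**Formula.** S(t) = ∏(1 − dᵢ/nᵢ) over event times up to t, where dᵢ is the number of recurrences and nᵢ the number at risk.

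**Recurrers only, as written.** With k recurrers, distinct event times and no censoring, the successive factors are (k−1)/k, (k−2)/(k−1), …, 0/1. The product after j events is (k−j)/k, which is 0 at j = k. Tied event times give the same end point. This holds for any k ≥ 1 and needs no assumed rate. If k = 0, the curve has no subjects.

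**All 35, recurrence-free subjects followed to day 365.** The risk set starts at 35 and S(365) = (35 − k)/35.

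| Recurrences (of 35) | Crude rate | Final S, recurrers only | S(365), all 35 |
|---|---|---|---|
| 1 | 2.9% | 0.000 | 0.971 |
| 2 | 5.7% | 0.000 | 0.943 |
| 4 | 11.4% | 0.000 | 0.886 |
| 7 | 20.0% | 0.000 | 0.800 |
| 11 | 31.4% | 0.000 | 0.686 |

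**A worked illustration.** Suppose 5 of 35 recur, on days 90, 150, 210, 270 and 330, and the other 30 are followed to day 365.
- Recurrers only: 4/5, 3/5, 2/5, 1/5, 0/5 = 80, 60, 40, 20, 0%.
- All 35: 34/35, 33/35, 32/35, 31/35, 30/35 = 97.1, 94.3, 91.4, 88.6, 85.7%.
- Gap at one year: 85.7 − 0 = 85.7, about 86 percentage points.

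**Unequal follow-up.** Take k = 7 and censor the 28 recurrence-free subjects evenly over days 90 to 365. Four recurrences have occurred by day 205, with 35, 32, 26 and 20 subjects at risk.
- All 35: S(205) = 34/35 × 31/32 × 25/26 × 19/20 = 0.860, a recurrence risk of 14.0%.
- Crude proportion at that day: 4/35 = 11.4%, which is too low because it treats subjects already out of observation as recurrence-free.
- Recurrers only: S(205) = 3/7 = 0.429, already past its median.

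**A caution for the corrected curve.** With k = 2 (days 60 and 350) and the same even censoring of the other 33, only 3 subjects are at risk at day 350. Then S(365) = 34/35 × 2/3 = 0.648, against a crude rate of 5.7%. One late event moves the tail a long way, so the curve needs numbers at risk and an interval beside it.

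**The case against.** The strongest defence is that the sentence is loose drafting for a curve on all subjects with recurrence as the event. The survival-analysis heading and the ITT rule in section 7 fit that reading, and the SAP refers to separate table and figure shells that may define the risk set. This is plausible. But 9.2.8 names its own narrower set and gives no censoring rule, and a programmer following it would filter to recurrers. If the intent was the full cohort, the correction simply records it.

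A second defence concerns weight. The study is descriptive ("No formal statistical testing will be performed"), recurrence is a secondary endpoint, the curve sits under the study-subjects heading rather than endpoint analysis, and crude recurrence incidence is still reported. All of that stands: the primary endpoint and every planned proportion are untouched, and cohort recurrence is not wholly undescribed. It does not rescue the curve, because a descriptive figure still has to describe the treated cohort, and the crude proportion makes no allowance for follow-up time.

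Three narrower points also stand. The 86-point gap comes from invented event times and arises only if the curve is read as cohort survival, although that is how such a figure is normally read. The documents name an onset date for adverse events but no explicit recurrence-date or last-contact field, and the study-exit form is described only as recording exit type. Finally, the SAP plans no confidence intervals elsewhere, so adding one goes beyond correcting the risk set. It is recommended because of the unstable tail shown above.

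**Conclusion.** The concern holds. As written, the curve is fixed at 0% from the last recurrence onward for any number of recurrers. It cannot distinguish a cohort with 1 recurrence in 35 from one with 11, where the full-cohort curve with complete follow-up ends at 97.1% and 68.6%. The fall to zero is an algebraic result and rests only on the literal wording of 9.2.8. The full-cohort values rest on assumed recurrence counts and, for the table, on complete one-year follow-up. The 86-point gap is an illustration, not a forecast. The defect is confined to this one output, but that output cannot be interpreted as recurrence risk and conflicts with the SAP's own population rule, so it should be corrected before the analysis is run.

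**What to change.** Replace the sentence in SAP 9.2.8 with wording such as:

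> Time from the index procedure to the first clinically confirmed hernia recurrence will be estimated by the Kaplan-Meier method in all ITT subjects. Subjects without recurrence will be censored at their last documented clinical contact, at most one year after the index procedure. The curve will show numbers at risk, and the one-year estimate will be given with a 95% confidence interval.

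Where few subjects remain at risk late in the year, the report should say so and not rest on the one-year figure alone. If the delay among recurrers is also wanted, a listing or median labelled as such would serve.

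The cost is a few lines of SAP text and no new patients. Before finalising, confirm that the eCRF holds a recurrence date and a last-contact date for every subject. The planned curve already presupposes the first. The second should come from visit dates in the charts being abstracted, though neither document names it as a field.

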#### 9.2.9 Safety and Complications

All complications during the index surgery, discharge and followup visits including Device Deficiency and Adverse Event will be summarized. By subject listings will be provided for each subject reported.

#### 9.3 Endpoint Analysis

Primary, Secondary, Teritory and Safety Endpoints will be analysed based on the surgery evaluation, Discharge and Follow-Up report.

#### 9.3.1 Analysis of the Primary Endpoints

The incidence of post-operative complications requiring procedural intervention within 90 days post index procedure.willbe summarized. The proportion of subjects with the incidents will be presented.

#### 9.3.2 Analysis of the Secondary Endpoints

The following incidents by subjects will be summarized: Incidence of early post-operative complications (Surgical Site Occurrences) within 90 days post index procedure (seroma, abscess,

dehiscence, hematoma, wound necrosis, ileus, fistula, delayed wound healing). Incidence of Surgical Site Infections (SSIs) within 90 days post index procedure. Incidence of later post-operative complications occurring after 90 days post index procedure. Incidence of hernia recurrence confirmed by clinical assessment. Incidence of reoperation requirement due to index repair.

#### 9.3.3 Analysis of the Teritory Endpoints

Average length of hospital stay (LOS) post index procedure (measured in days) and rate of opioid usage following procedure as determined by % of prescriptions filled and refilled will be summarized and presented.

#### 9.3.4 Analysis of Device Deficiency

Device deficiencies will be presented by the nature of the device deficiency (e.g. mechanical failure, shunt pathway obstruction, etc.). Each device deficiency will be summarized on a patient basis by tabulating the counts and percentages of subjects with the deficiency. For the patient-based results, a deficiency which occurred multiple times for the same patient will only be counted once. Device deficiency will also be presented on a deficiency basis, where the number of occurrences of each deficiency will be presented. The analysis of device deficiencies will be performed in the enrolled population. By subject listings will be provided for each subject reported.

#### 9.3.5 Analysis of Adverse Events

The incidence rate of each of the adverse device effects through Index Surgery, Discharge and follow-up visit will be presented. The incidence of adverse events and serious adverse events will be tabulated (frequencies and percentage of patients) by severity and relationship to device and procedure. The analysis of safety will be performed in the enrolled population.

Descriptive statistics will be provided for safety endpoints by surgical procedure. All safety summaries will be presented for the full analysis population. Adverse Device Events will be coded according to Medical Dictionary for Regulatory Activities (MedDRA) AE coding dictionary. All ADEs will be listed. A summary of the frequency count and percentage of subjects reporting each ADE category will be produced for all reported ADEs and SADEs. Relationship of AE verbatim text to group terms and body systems will also be reported. A listing of withdrawals due to ADEs will be provided. Deaths and SADEs will be listed should they occur.

AE listing includes Onset Date, AE Term, Relation to Device, Relation to Procedure, Pattern, Seriousness (SAE), Severity, Treatment, Medication, Surgical, Outcome, End Date. By subject listings will be provided for each subject reported.

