## 10.4.6 Safety Analyses

All AEs will be coded using the Medical Dictionary for Regulatory Activities (MedDRA) and presented in by-subject listings. The number and percent of subjects experiencing any AE, any related AE, and discontinuations due to an AE will be tabulated. Treatment-emergent AEs will be tabulated (frequencies and percentages) by Preferred Term (PT) within System Organ Class (SOC). If a subject experiences more than one occurrence of the same AE, and these differ in severity and/or causality, the AE will be tabulated according to the greatest severity and nearest relationship to the device. A listing of subjects who withdraw from the study due to AEs will be presented, and the incidence of AEs leading to study discontinuation will be summarized. Deaths and SAEs will be listed should they occur.

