#### 3. STUDY OBJECTIVES

The primary objective of this study is to capture existing clinical performance data to confirm the continued performance of the Gentrix® Surgical Matrix. The safety objective of this study is to capture existing Gentrix® Surgical Matrix Complication data in the immediate post-operative period of 90 days. Existing clinical data support the safety and performance of the Gentrix® Surgical Matrix. There are currently no safety concerns with these products. This clinical investigation will confirm the safety and performance of the Gentrix® Surgical Matrix and identify any unknown side-effect.

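### SAP 9.3.5 confines to device-related events four safety outputs that Protocol 10.4.6 requires for all adverse or serious adverse events

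*SAP*

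**What the plan says.** Protocol 10.4.6 sets the safety outputs without a causality filter. On coding: "All AEs will be coded using the Medical Dictionary for Regulatory Activities (MedDRA) and presented in by-subject listings". It then asks for treatment-emergent AEs by preferred term within system organ class, a listing of subjects who withdraw because of AEs, and, for serious events, "Deaths and SAEs will be listed should they occur".

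SAP 9.3.5 covers the same ground with a different scope. Coding: "Adverse Device Events will be coded according to Medical Dictionary for Regulatory Activities (MedDRA) AE coding dictionary". Frequencies by type: "A summary of the frequency count and percentage of subjects reporting each ADE category will be produced for all reported ADEs and SADEs". Serious events: "Deaths and SADEs will be listed should they occur". The withdrawal listing is likewise limited to adverse device effects (ADEs).

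The same SAP section has two statements that do cover all AEs: "The incidence of adverse events and serious adverse events will be tabulated (frequencies and percentage of patients) by severity and relationship to device and procedure", and "Relationship of AE verbatim text to group terms and body systems will also be reported". It also specifies an AE listing with columns for term, relation to device, relation to procedure and seriousness.

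Both documents (Protocol 3.1 and SAP 3) say that the study will "identify any unknown side-effect".

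**The concern.** Protocol Table 2 defines an ADE as an AE related to use of the device. A side effect that nobody yet links to the device therefore falls outside the SAP's coding and type-specific frequencies. Those outputs depend on the attribution having been made already, which is the step that a search for unknown effects should not presuppose.

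One protocol rule makes this more than a remote case. Under 7.2.3, complications of routine procedures that the plan does not impose are classed as not related. Section 5.7.2 says that the study adds no procedures beyond standard care, so the rule could apply often.

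The practical risk lies in programming. Protocol section 10 leaves the detailed methods to the SAP, so the narrower text is the one likely to be built. Chart terms that are not coded can also split one event type across several wordings, which makes a small cluster harder to see in a listing.

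**Working it through.** The plan gives no figure to reproduce here, so the check is a comparison of Protocol 10.4.6 with SAP 9.3.5.

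| Output | Protocol 10.4.6 | SAP 9.3.5 |
|---|---|---|
| MedDRA coding | all AEs | adverse device events |
| Frequencies by event type | treatment-emergent AEs, by preferred term within system organ class | ADE categories, for ADEs and serious ADEs (SADEs) |
| Serious-event listing | deaths and SAEs | deaths and SADEs |
| Withdrawal listing | due to AEs | due to ADEs |

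The same substitution occurs four times. SAP 2 says that the plan is based on Protocol Version 1.0, and it gives no reason for a change of scope.

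Next, trace an event judged not related to the device through everything the SAP specifies:

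1. **AE listing (9.3.5).** The event appears, with its term, both relationships and seriousness.
2. **Severity-by-relationship table (9.3.5).** It is counted, but the sentence names no breakdown by event type.
3. **Verbatim-to-body-system report (9.3.5).** Its term is mapped, but no counts or percentages are specified. The mapping also fits poorly with coding only device events.
4. **Complications summary (9.2.9).** AEs are to be summarised, with no layout, coding or event type stated.
5. **Endpoint summaries (9.3.1 and 9.3.2).** No causality filter applies. The event is counted if it meets an endpoint: a complication requiring a procedural intervention, one of the eight named surgical site occurrences, a surgical site infection, a late complication, a recurrence or a reoperation. Only some of these name an event type.
6. **ADE/SADE frequency table, death/SADE listing and ADE withdrawal listing (9.3.5).** It is absent, unless it is a death.

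So the event is visible case by case, but is assured of a frequency by type only if it is one of the named complications.

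The result does not depend on how the collection conflict is resolved. Protocol 7.2.1 requires all AEs. Protocol 7.3.1 requires only those potentially related to the device or procedure. Even under 7.3.1, events attributed to the procedure alone are recorded and are not ADEs.

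For scale, take n = 35 (Protocol 10.2, SAP 8) and true per-subject event rates p of 2%, 5% and 10%. These rates are assumptions; the documents give none.

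- P(at least one case) = 1 − (1 − p)^35: 50.7%, 83.4%, 97.5%.
- P(two or more) = 1 − (1 − p)^35 − 35p(1 − p)^34: 15.5%, 52.8%, 87.8%.

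At the lower assumed rates, a new effect would probably show as one case or a few. A table of all AEs by type puts such cases in one row whatever the attribution.

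**The case against.** The strongest reply is that little is hidden. With about 35 subjects, a listing that shows term, relationship and seriousness can be read line by line. The SAP also maps AE terms to body systems, summarises AEs among complications, and reports several complication endpoints whatever their cause. SAP 9.3.5 mixes AE and ADE wording and nowhere says that other AEs will not be coded, so this may be loose drafting.

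Much of that stands, and it rules out several stronger readings that a reader might infer:

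- *Unrelated serious events drop out of the listings.* They do not. Only the dedicated listing is narrowed; the AE listing carries a seriousness column.
- *Such events appear in no output grouped by type.* This is too absolute, given the body-system mapping and the named complications.
- *Everything turns on one investigator's judgement.* Protocol 7.2.3 gives causality to the sponsor and the investigator, and sends unassessable or uncertain cases to the possible category. Whether a possible event counts as an ADE is undefined in the SAP, so this safeguard is incomplete.
- *A full table would reveal an excess.* The study has a single arm and states no reference rates for AEs. The table would show counts, not an excess.

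What the reply does not remove is the missing table of all AEs by type and the narrowed serious-event listing. A readable listing is not a substitute for outputs that the protocol requires, and four parallel substitutions are hard to treat as one slip.

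**Conclusion.** The point holds as a conflict of scope between the two documents: four outputs required for all AEs or SAEs are confined in the SAP to device-related events. The effect is that an event judged not device-related is assured of a listing line and a severity-by-relationship count, but not of a frequency by event type unless it is a named complication.

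A reader might infer that the aim of finding unknown side effects cannot be met. The documents do not support that, because the cases remain visible in the AE listing; the aim is weakened. The primary endpoint analysis is unaffected, as it has no causality filter. The withdrawal listing probably matters least in a chart review.

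The conclusion assumes that SAP 9.3.5 is programmed as written. The number of events affected cannot be stated, because the documents give no expected AE rates or attribution split.

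**What to change.** In SAP 9.3.5:

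- Code all AEs in MedDRA.
- Tabulate subjects by preferred term within system organ class for all AEs and all SAEs, with ADE and SADE columns as subsets.
- List deaths and all SAEs, with SADEs flagged.
- List withdrawals due to any AE.
- State which of the causality levels in Protocol 7.2.3 make an event an ADE, and in particular how possible events are treated.

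Reconcile Protocol 7.2.1 with 7.3.1 on which events are recorded, because the SAP change can tabulate only what reaches the database.

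The cost is SAP wording, a revised table layout and coding a few additional terms in about 35 subjects. No further data collection follows if all AEs are already being recorded. If the site has followed 7.3.1, events unrelated to both device and procedure may be missing, and the SAP change alone would not recover them.
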